**Blinding:**

This is an open-label study.

**IP Administration Procedure:**

IA injections will be performed by the assigned injector. The injector may choose the position of the knee (e.g., extended or flexed), the approach for the injection (e.g., medial or lateral) and the numbing agent to be used (e.g., ethyl chloride, subcutaneous lidocaine; IA anesthetics are not allowed) based on standard of care. Sterile technique should be used.

Prior to injection, the index knee should be thoroughly cleansed using a bactericidal solution. The index knee will be aspirated in all cases prior to administration of study medication. Following attempted aspiration, 5 mL of the reconstituted FX006 will be injected into the synovial space. Refer to the Pharmacy Binder for detailed instructions on how to prepare FX006.

The same needle used for IA injection of the study medication may also be used for synovial fluid aspiration, thereby allowing for a single injection with syringe replacement. The injector will use a 21 gauge or larger needle for injection and aspiration of fluid.

Patients should be advised to avoid strenuous activities or prolonged weight-bearing activities for approximately 24 to 48 hours following the injection and to also maintain a stable lifestyle with regard to physical activity throughout the duration of the study.

In the event that the patient has an immediate reaction (e.g., tenderness, increased pain, swelling, effusion, decreased mobility of the index knee), the patient should be treated according to local clinical guidelines and physician experience

**Concomitant Medications:**

The exclusion criteria indicate that a patient may not be enrolled if he/she has used any of the following within the specified windows. In addition these medications should not be taken or used throughout the study:

- IV, IM or oral corticosteroids
- IA corticosteroids in any joint
- IA viscosupplementation (hyaluronic acid) or any IA intervention (IA injection, IA aspiration, etc.) in the index knee
- Opiates
- Any investigational drug, device or biologic
- Immunomodulators, immunosuppressives, or chemotherapeutic agents
- Live or live attenuated vaccines

**Criteria for Evaluation:**

***Safety Variables***

Safety and tolerability will be evaluated on the basis of AEs spontaneously reported by the patient or discovered by the Investigator and findings from the following assessments: physical examinations, index knee assessments, vital signs, and clinical laboratory evaluations. In addition the index knee will be evaluated by X-ray and assessed by a central imaging vendor for joint space narrowing, chondrolysis, subchondral bone changes, bone infarcts, avascular necrosis, joint swelling, and insufficiency fracture.

***Exploratory Efficacy Variables***

- Western Ontario and McMaster Universities (WOMAC®) Osteoarthritis Index (Likert (LK) 3.1, 5-point scale): pain, stiffness and function domains independently and collectively ([Bellamy et al, 1988](#)).
- Knee injury and Osteoarthritis Outcome Score (KOOS) Quality of Life (QOL) Subscale
- Daily activity measured as steps per day
- Global Physical Activity Questionnaire (GPAQ) domains for Occupational physical activity, Transport-related physical activity, and Physical activity during discretionary or leisure time)

**Sample Size Considerations:**

A sample size of approximately 100 patients who receive two doses of 32 mg FX006 is considered a reasonable sample size in order to assess the safety profile of repeat administration of FX006. No formal power and sample size calculations have been made as the analysis of the efficacy data collected from this study will be considered exploratory and hypothesis-generating for future multiple dose studies of FX006. In order to ensure at least 100 patients who receive two doses of 32 mg FX006 are enrolled and followed for 52 weeks, approximately 200 patients will be enrolled based on an estimate that approximately 66% of patients enrolled will be eligible to receive a second dose of 32 mg FX006 and approximately 75% of subjects who receive a second dose will complete the study through Week 52.

**Statistical Methods:**

A comprehensive statistical analysis plan (SAP) will be written and approved prior to database lock for this study that describes the final analyses to be completed for safety and exploratory efficacy endpoints.

No formal interim analysis is planned for the primary safety endpoints in this open-label study to assess the safety and tolerability of FX006 after repeat administration. However, interim analysis may be conducted with exploratory endpoints to examine efficacy signals following administration of one or two doses of 32mg FX006. These interim analyses on exploratory endpoints may be completed for data review, regulatory updates, and/or publication (or presentation at congresses) for this open-label study. Any interim analysis completed will have an interim analysis plan written and approved to describe the purpose and analytical objectives of the interim analysis. Final analyses, described in the protocol and statistical analysis plan, will be conducted after completion of the study, when all subjects have either discontinued the study early (prior to Week 52) or completed the study through Week 52.

Demographic and baseline characteristics will be listed by study site and patient, and will be summarized by treatment. Frequencies and proportions will be presented for the categorical variables and descriptive statistics will be presented for continuous variables.

Treatment exposure will be listed by study site and patient, and will be summarized by treatment and dose.

The examination of efficacy is exploratory in this study. Data from the WOMAC® questionnaire will be presented in by-patient listings with summary presentation of the data and exploratory analyses.

Analysis of the magnitude of pain relief observed with WOMAC A (pain), stiffness (WOMAC B), and function (WOMAC C) will be explored between patients who receive one dose and those receiving a second following the first and second doses of 32 mg FX006 will be explored with a mixed model for repeated measures (MMRM) with fixed effects of number of doses (1 or 2) received, and a dose by time interaction. Model covariates will include study site, and potentially other variables. Subject will be a random effect in the model. Time points of interest for this analysis are those when a subject is eligible for a second dose.

A second within subject analysis will be completed for subjects who receive two doses of FX006 to examine the improvement in WOMAC scores within a subject after receiving the second dose: WOMAC after the first dose, compared to WOMAC following the second dose. The change from baseline to the last WOMAC score for the first dose will be compared to the change from the last score prior to the second dose to the last WOMAC score following the second dose. The increment difference in the overall change for the first dose compared to second dose will be explored with a linear model.

Evaluation of dose-response will be assessed descriptively with an examination of WOMAC A responses at the time (in weeks) of second dose administration to assess the magnitude of scores at each week that a second dose may be administered. The time to maximal pain relief response with WOMAC A following the first and second doses of 32 mg FX006 will be examined using a Kaplan-Meier (KM) procedure.

Questionnaire data from the Global Physical Activity Questionnaire (GPAQ) domains (occupational physical activity, transport-related physical activity, and physical activity during discretionary or leisure time) will be described descriptively at the two time points collected (Screening and Week 12). The change in GPAQ domain scores and total score will be examined with an analysis of variance (ANOVA) model with summaries comparing patients who receive one dose to those receiving two doses of 32 mg FX006. GPAQ information collected at Screening will be utilized to normalize steps per day based on lifestyles activity. GPAQ information will be a model covariate in subsequent analyses.

AEs will be coded using the Medical Dictionary for Regulatory Activities (MedDRA) dictionary. Incidences (number and percent) of treatment-emergent adverse events (TEAEs), those events that started after dosing or worsened in severity after dosing, will be presented by treatment group. Incidences of TEAEs will also be presented by maximum severity and relationship to study medication.

Similar presentations will be provided for serious AEs, AEs leading to withdrawal from the study, or AEs leading to death. Analysis of AE data will include examination of the incidence rates of TEAEs and index knee related TEAEs following the first dose and second dose, as well as the cumulative incidence of TEAEs after all doses of 32 mg FX006. Both the number of events and the number of patients experiencing an event will be examined to assess the by patient cumulative incidence of TEAEs associated with repeat administration.

Clinical laboratory data and vital sign information will be presented as descriptive summary statistics for value and change from Baseline at each individual time point.

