#### **9.4.4. Safety Analyses**

AEs will be coded using the Medical Dictionary for Regulatory Activities (MedDRA) dictionary. Incidences (number and percent) TEAEs, those events that started after dosing or worsened in severity after dosing, will be presented by treatment group. Incidences of TEAEs will also be presented by maximum severity and relationship to study medication. Similar presentations will be provided for serious AEs, AEs leading to withdrawal from the study, or AEs leading to death.

Analysis of AE data will include examination of the incidence rates and changes in severity of TEAEs and index knee related TEAEs following the first dose and second dose, as well as the cumulative incidence of TEAEs after all doses of FX006. Both the number of events and the number of patients experiencing an event will be examined to assess the by patient cumulative incidence of TEAEs associated with repeat administration. The cumulative TEAE incidence rate will also be compared with total exposure to FX006.

Clinical laboratory data and vital sign information will be presented as descriptive summary statistics for value and change from Baseline at each individual time point.

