#### 4.10.1. Adverse Events

Adverse events will be coded using the MedDRA (version 19.1) coding system and displayed in tables and data listings using system organ class (SOC) and preferred term (PT).

Analyses of AEs will be performed for those events that are considered treatment-emergent, where treatment-emergent is defined as any AE with onset after the administration of study treatment, or any event that was present at baseline but worsened in intensity through the end of the study.

If the start date/time of an AE is partially or completely missing, the date/time will be compared as far as possible with the date/time of the start of administration of study drug. The AE will be assumed to be treatment emergent if it cannot be definitively shown that the AE did not occur or worsen during the treatment-emergent period (worst case approach). The following general rules will be used:

- If the start time of an AE is missing but the start date is complete, an AE will only be excluded as being treatment emergent if the start date is before the date of study drug administration or if the stop date/time is before study drug administration.
- If the start time and day are missing but the start month and year are complete, an AE will only be excluded as being treatment emergent if the start month/year is before the month/year of study drug administration or if the stop date/time is before study drug administration.
- If the start day and month are missing but the start year is complete, an AE will only be excluded as being treatment emergent if start year is before the year of study drug administration or if the stop date/time is before study drug administration.
- If the start date is completely missing, an AE will be considered treatment-emergent unless the stop date/time is before study drug administration.

Adverse events will be summarized by patient incidence rates; therefore, in any tabulation, a patient contributes only once to the count for a given SOC or preferred term.

Summary tables will display the number and percentage of patients who experienced at least one TEAE in each of the following categories:

- Any TEAE
- Any Serious Adverse Event (SAE)
- Any TEAE leading to study discontinuation
- Any TEAE by severity (grade 1-5)
- Any TEAE by relationship
- Any index-knee related TEAE
- Any index-knee related SAE
- Any index-knee related TEAE leading to study discontinuation

- Any index-knee related TEAE by severity (grade 1-5)

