- Any index-knee related TEAE by relationship
- Any TEAE related to injection procedure

Separate tabulations will be produced for each of following categories:

- All TEAEs by SOC and PT
- All SAEs by SOC and PT
- All TEAEs related to study drug by SOC and PT
- All TEAEs related to injection procedure by SOC and PT
- All TEAEs by maximum severity by SOC and PT
- All TEAEs leading to study discontinuation
- All TEAEs leading to death
- All index-knee related TEAEs by SOC and PT
- All index-knee related TEAEs related to study drug by SOC and PT
- All index-knee related TEAEs by maximum severity by SOC and PT

Summary tables and the tabulation of All TEAEs by SOC and PT will be presented for the following patient groups and time periods, with a separate table for each patient group:

1. Patients receiving only one dose
  - a. First dose to Week 12
  - b. First dose to Week 24 (end of study)
2. Patients receiving the second dose at Week 12
  - a. First dose to Week 12
  - b. Week 12 to Week 24
  - c. Week 12 to Week 52
3. Patients receiving the second dose at Week 16
  - a. First dose to Week 16
  - b. Week 16 to Week 32
  - c. Week 16 to Week 52
4. Patients receiving the second dose at Week 20
  - a. First dose to Week 20
  - b. Week 20 to Week 40
  - c. Week 20 to Week 52
5. Patients receiving the second dose at Week 24
  - a. First dose to Week 24
  - b. Week 24 to Week 48
  - c. Week 24 to Week 52

Summary tables and all tabulations will be presented for the following time periods for patients receiving two doses only (same table):

1. Baseline to Week 52
2. Baseline to Week 12
3. Second dose to 12 weeks after second dose

Date and time of onset of TEAE will be used to assign the time periods.

In the summary table for "Any TEAE by SOC and PT", an additional row with the number of events observed will be presented. A patient will be counted once for the number of patients if they have multiple events. The total number of events will be the absolute number of events observed, and a patient will be counted more than once for the event totals if they have multiple events.

In these tabulations, related is defined as any TEAE deemed possibly, probably or definitely related to study drug by the investigator. If relationship is missing, it will be imputed as related.

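### The SAP plans no event count for index-knee TEAEs, although the protocol singles them out by dose and calls for event as well as patient counts of TEAEs

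*Protocol*

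**What the plan says.** **Protocol, Section 2 (Synopsis), Statistical Methods.** One sentence sets the event types and the doses: "Analysis of AE data will include examination of the incidence rates of TEAEs and index knee related TEAEs following the first dose and second dose". It also asks for cumulative incidence after all doses. The next sentence sets the counting units: "Both the number of events and the number of patients experiencing an event will be examined to assess the by patient cumulative incidence". The object of that sentence is TEAEs that go with repeat administration. It does not name the index knee.

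**Protocol, Section 9.4.4.** The same pair of sentences, with severity added to the first: "incidence rates and changes in severity of TEAEs and index knee related TEAEs following the first dose and second dose", followed by "Both the number of events and the number of patients experiencing an event will be examined".

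**SAP, Section 4.10.1.** The default unit is the patient: "Adverse events will be summarized by patient incidence rates; therefore, in any tabulation, a patient contributes only once to the count". The rule applies within each SOC and each PT. There is one exception. For the table of any TEAE by SOC and PT, "an additional row with the number of events observed will be presented", and there "a patient will be counted more than once for the event totals if they have multiple events". The section also plans three index-knee tables by SOC and PT (all, drug-related, maximum severity) and several index-knee lines in the summary table. None has an event count.

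**Periods.** For two-dose patients pooled, the summary tables and all tabulations cover Baseline to Week 52, Baseline to Week 12, and the 12 weeks after the second dose.

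**SAP, Section 5.** Two changes from the protocol are declared: the one-dose versus two-dose comparisons are dropped, and the Kaplan-Meier analysis is redirected to time to second dose. Counting of adverse events is not mentioned.

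**The concern.** The primary objective is the safety and tolerability of repeat administration, and both injections go into the same knee. With the one-dose versus two-dose comparison removed, the pooled two-dose periods are where the plan sets the knee's response to the first dose beside its response to the second.

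A patient-once count answers how many patients had a knee event. It does not answer how many knee events there were. If the second injection brought several reactions in the same patients, the share of patients affected could stay the same while the number of events rose. The protocol's request for both counts guards against this, and the SAP meets that request only for TEAEs of all kinds together.

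**Working it through.** No figure in the plan has to be reproduced; this is a comparison of texts, followed by an illustration of size.

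**1. Which tables count events?** Under SAP Section 4.10.1, only the all-TEAE table by SOC and PT.

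**2. Can knee events be recovered from that table?** No. Its rows are SOCs and PTs, and a PT need not identify the joint. Protocol Section 5.2.8, for example, reports arthralgia in any joint. The event total includes index-knee events but does not separate them.

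**3. What do the index-knee tables hide?** Take three constructed patients, all with the same PT, second dose at Week 12, and no knee event later than 12 weeks after it. The rule of one count per patient per period gives:

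| Patient | Events after dose 1 | Events after dose 2 | Total events | Count, Baseline to Week 12 | Count, 12 weeks after dose 2 | Count, Baseline to Week 52 |
|---|---|---|---|---|---|---|
| A | 1 | 0 | 1 | 1 | 0 | 1 |
| B | 1 | 1 | 2 | 1 | 1 | 1 |
| C | 1 | 3 | 4 | 1 | 1 | 1 |

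- A and B differ in the second-dose column, so a flare after each dose does reach the tables, though the two columns are not linked by patient.
- B and C print identically in all three columns, with 2 and 4 events.
- In the Baseline to Week 52 column all three print identically, with 1, 2 and 4 events.
- Events with different PTs would still appear in separate PT rows. Only repeats of the same PT collapse there; at SOC level all repeats within the SOC collapse.

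**4. How large could the loss be?** The documents give no index-knee TEAE rate for two doses and no distribution of events per patient. Protocol Section 5.2.8 gives two single-dose rates for FX006 that can stand in as assumptions: arthralgia in any joint 67/687 = 9.8%, and joint swelling 19/687 = 2.8%. Let p be the share of patients with at least one event and m the mean number of events per patient.

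- No clustering (Poisson): m = -ln(1 - p).
- Clustering (negative binomial with dispersion k, smaller k meaning more clustering): m = k[(1 - p)^(-1/k) - 1].
- Events per affected patient = m/p.

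At p = 0.098, per 100 patients (9.8 affected):

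| Model | Events | Events per affected patient |
|---|---|---|
| Poisson | 10.3 | 1.05 |
| k = 0.5 | 11.5 | 1.17 |
| k = 0.2 | 13.5 | 1.38 |
| k = 0.1 | 18.1 | 1.84 |

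At p = 0.028 the range from Poisson to k = 0.1 is 1.01 to 1.17. At p = 0.20, a rate no document gives, it is 1.12 to 4.16. Every model at a given p prints the same patient percentage, so the planned index-knee tables cannot show which one holds.

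**The case against.** **The protocol does not expressly ask for this.** A reader might infer that the protocol commits to event counts for index-knee TEAEs dose by dose and that the SAP breaks the commitment. The text does not go that far. The event-count sentence speaks of TEAEs, and the index knee and the two doses are named only in the sentence before. Read literally, the event row in the all-TEAE table satisfies it. This stands. It remains reasonable to read the two sentences together, because index-knee TEAEs are TEAEs and have just been singled out.

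**Much of the information is available.** A reader might also infer that repeat knee reactions disappear from the tables serving the primary objective. They do not. The all-TEAE table serves that objective for the same periods and includes knee events in its total. A patient with a flare in each 12-week window counts in both columns. Index-knee severity and relationship are tabulated, and SAP Section 4.2.1 puts all collected data in listings. This stands too, but a listing is not a summary, and none of these gives a number of index-knee events.

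**The loss may be slight.** This is fair. A doubling of events behind an unchanged percentage can only be assumed; nothing in the documents shows it.

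**The shells are not available.** SAP Section 4.2.1 places the mock shells in a separate document, which may already carry the row.

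The point does not extend to SAEs. The protocol asks for number and percent there, and the SAP gives SAEs their own by-patient listing.

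**Conclusion.** The point holds in a limited form. As the SAP is written, no index-knee table shows repeats of the same event in one patient within a period, or the cumulative number of knee events over Baseline to Week 52. SAP Section 1.2.2 says the SAP will set out differences from the protocol's planned analyses, and Section 5 neither declares nor explains this one. It is better described as an unexplained narrowing of a reasonable reading than as a breach of an explicit commitment.

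The size is unknown. On the assumed single-dose rates the loss runs from almost nothing (1.01 events per affected patient) to 1.84 under heavy clustering. Those rates are not index-knee rates after two doses, and the dispersion values are assumptions. The conclusion about the tables depends on neither; it rests on the SAP's counting rule and on the shells not already containing the row. This is a cheap improvement, not a flaw that undermines the safety analysis.

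**What to change.** In SAP Section 4.10.1, extend the number-of-events row to the table of all index-knee related TEAEs by SOC and PT, for the three pooled two-dose periods: Baseline to Week 12, second dose to 12 weeks after it, and Baseline to Week 52. Ideally add one line per period giving the number of patients with 0, 1, 2 and 3 or more index-knee TEAEs, which would show clustering directly. If the shells already carry the row, align the SAP text with them. If the sponsor prefers patient counts only, say so in Section 5 with the reason.

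Cost: a sentence in the SAP, a change to the shells and a few table rows. No new data are needed. The downside is slightly longer tables.
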